----------------------------	---

Clinical Trial Protocol

Page 7 of 140

Proprietary confidential information © 2022 Boehringer Ingelheim International GmbH or one or more of its affiliated companies

	
IMV cohort, adjustment will be made for the baseline WHO value, baseline D-Dimer level and age.
 
For each of the two key secondary endpoints, treatment failure at Day 28 and all cause mortality at Day 28, the delta method and average marginal effect method will be used to calculate the risk difference, 95% confidence intervals and p-values. Adjustment will be made for the same set of covariates as in the primary analysis of the primary endpoint.
 
Descriptive statistics will be used to analyse all other endpoints and for all analyses of the IMV patient cohort.
 
If the NIV and IMV patient cohorts show homogeneity, then a meta-analysis will be performed to obtain an overall treatment estimate, albeit in an exploratory manner.

--	---

Clinical Trial Protocol

Page 8 of 140

Proprietary confidential information © 2022 Boehringer Ingelheim International GmbH or one or more of its affiliated companies

FLOW CHART

Trial Periods	Screening	Intravenous open-label treatment					Follow-Up			
Visit number	1	2a	2b	2c	2d	2e / EOT	3	4	5	6 / EOS
Day	0	1	2	3	4	5	6	7	28	90
Hours	-24 - 0	0-14	26-38	50-62	74-86	98-110	134			
Time windows [hrs, if not specified otherwise]		+6	±2	±2	±2	+6	±12	+1 day	+2 days	±7 days
Informed consent (separate IC for patients participating in PK sampling)	X									
Demographics	X									
Medical history	X									
Physical examination	X					X			X	
Weight	X									
Height	X									
Vital signs ¹	X	X	X	X	X	X	X	X	X	
12-lead ECG ²	X	(X only needed in case of clinical event) ²								X
Review of in-/exclusion criteria	X									
IRT call	X	X				X				
Randomisation ³		X								
Dispense trial drugs	X									
Administer trial drug ⁴		X	X	X	X	X				
PK Sampling ⁵		X								
Laboratory Tests ⁶	X			X		X	X ⁶		X	
D-dimer assessment ⁷	X			X		X		X	X	
Fibrinogen, aPTT and antithrombin assessment ⁸	X	X	X	X	X	X	X	X	X	
PaO ₂ /FiO ₂ ratio (or inferred PaO ₂ /FiO ₂ ratio from SpO ₂) ⁹	X	X	X	X	X	X	X	X	X	

Trial specific examinations: SOFA score ¹⁰	X						X		X	
11-point WHO Clinical Progression Scale (see Section 5.1.1) ¹¹	X	X	X	X	X	X	X	X	X	
Pregnancy testing ¹²	X								X	
SARS-CoV-2 test ¹³	X									
All adverse events/Serious adverse events ¹⁴	X	X	X	X	X	X	X	X	X	
Concomitant therapy	X	X	X	X	X	X	X	X	X	

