3.3.2 Inclusion criteria

Patients participating in Part 1 are not eligible for Part 2.

1. Age \geq 18 years-(or above legal age)
2. ARDS with $\text{PaO}_2^*/\text{FiO}_2$ ratio >100 and ≤ 300 , either on non-invasive ventilator support, OR on mechanical ventilation (<48 hours since intubation),
 - with bilateral opacities in chest X-ray or CT scan (not fully explained by effusions, lobar/lung collapse, or nodules)
 - with respiratory failure (not fully explained by cardiac failure/fluid overload)

*or estimation of $\text{PaO}_2/\text{FiO}_2$ from pulse oximetry ($\text{SpO}_2/\text{FiO}_2$) (see [Appendix 10.2](#) for $\text{SpO}_2/\text{FiO}_2$ estimation)
3. SARS-CoV-2 positive (laboratory-confirmed RT PCR test)
4. Fibrinogen level \geq lower limit of normal (according to local laboratory)
5. D-Dimer \geq upper limit of normal (ULN) according to local laboratory
6. Signed and dated written informed consent in accordance with ICH Good Clinical Practice (GCP) and local legislation prior to admission to the trial.

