7. STATISTICAL METHODS AND DETERMINATION OF SAMPLE SIZE

The eligible patients for this trial will be randomised in Part 1 to one of three treatment arms

- alteplase 0.3mg/kg over 2 hours, followed by daily long-term (12h) infusion of 0.02 mg/kg/h over 5 days, “alteplase dosing regimen A”
- alteplase 0.6mg/kg over 2 hours, followed by daily long-term (12h) infusion of 0.04 mg/kg/h over 5 days, “alteplase dosing regimen B”
- standard of care

in a 1:1:1 ratio, stratified according to ventilation (invasive mechanical vs. non-invasive).

In Part 2, patients will be randomised to

- alteplase (one dosing regimen), depending on results of Part 1. Accordingly, the following dosing regimen will be carried forward in Part 2: alteplase 0.6mg/kg over 2 hours, followed by daily long-term (12h) infusion of 0.04 mg/kg/h over 5 days, “alteplase dosing regimen B”
- standard of care

in a 2:1 ratio, stratified according to baseline ventilation status (invasive mechanical vs. non-invasive) and baseline D-Dimer level (\geq ULN to <5 vs \geq 5-fold ULN).

Throughout this whole Section, the NIV (non-invasive ventilation) patient cohort are those with a baseline WHO value of 6, and the IMV (invasive mechanical ventilation) patient cohort are those with a value 7, 8 or 9 at baseline.

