7.1 NULL AND ALTERNATIVE HYPOTHESES

Throughout this Section, alteplase refers to the randomised treatment group, which is in addition to SOC. With regards to Part 1, reference will be made to alteplase dosing regimen A and alteplase dosing regimen B and in Part 2, reference will be made to alteplase.

The primary endpoint related to Part 1, secondary endpoints, [REDACTED] will be evaluated in an exploratory manner.

For Part 2:

The primary objective of the statistical analysis is to determine whether alteplase significantly increases the chances of clinical improvement or hospital discharge up to Day 28, in comparison to SOC alone. The key secondary objectives of the statistical analysis are to determine whether alteplase significantly prevents treatment failure (defined as WHO value \geq 7) at Day 28, or all cause mortality at Day 28, in comparison to SOC alone.

For the primary analysis of the primary endpoint a Cox proportional hazards model will be used. In the NIV patient cohort, adjustment will be made for the number of days under NIV support, baseline D-Dimer level and age. For the IMV patient cohort, adjustment will be made for the baseline WHO value, baseline D-Dimer level and age.

For the primary analysis of the key secondary endpoints, the delta method and average marginal effect method will be used to calculate the risk differences, the 95% confidence intervals and p-values. Adjustment will be made for the same set of default covariates as in the primary analysis of the primary endpoint.

In line with the primary and key secondary objectives of the statistical analysis, a confirmatory hierarchical testing procedure will be applied for the following set of hypotheses, in the NIV patient cohort, in the following order:-

H0_1:

The null hypothesis to be tested for the primary endpoint in the NIV patient cohort is that the hazard ratio between alteplase and SOC alone equals 1 for all $t > 0$. The alternative hypothesis is that the hazard ratio between alteplase and SOC alone is not equal to 1 for all $t > 0$. Superiority will be declared if the hazard ratio between alteplase and SOC alone is significantly greater than 1 at the two-sided type I error level alpha=5%.

H0_2:

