7.2 PLANNED ANALYSES

7.2.1 General considerations

With regards to each efficacy and safety endpoint, the term "baseline" refers to the last observed measurement prior to randomisation for all patients.

The statistical analysis will be based on the following populations:

The Randomised Set (RS) will consist of all randomised patients.

The Full Analysis Set (FAS) will consist of all randomised patients with at least one baseline and one post baseline assessment relating to the primary endpoint of interest - refer to [Section 2.1.2](#) for primary endpoints related to Part 1 and Part 2.

The Treated Set (TS) will consist of all patients who were randomised and, for patients in the alteplase groups, treated with at least one dose of trial drug.

Per Protocol Set (PPS) will consist of all patients in FAS who were without important protocol deviations (IPDs) for efficacy. The definition of IPDs will be specified in the Trial Statistical Analysis Plan (TSAP) but this PPS will only be determined for Part 2.

All endpoints will be presented for Parts 1 and Part 2 separately, and at the end of Part 2 most endpoints will additionally be pooled for descriptive purposes.

All analyses for all endpoints, both inferential and descriptive, including safety, will be performed on the NIV patient cohort, and the IMV patient cohort separately. This is in line with the statistical objectives of the study.

For selected endpoints, if homogeneity between the two patient cohorts is observed, combined treatment estimates will be determined using suitable meta-analysis techniques. These will be outlined in more detail in the Trial Statistical Analysis Plan.

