7.2.2 Primary endpoint analyses

For primary endpoints related to Parts 1 and 2, refer to [Section 2.1.2](#). The primary analyses will be performed on the FAS with treatment assignments as randomised.

Part 1

The primary endpoint for Part 1 will be analysed in a similar manner to Part 2, albeit in Part 1 this will be exploratory in nature, comparing alteplase dosing regimen A to SOC alone, and alteplase dosing regimen B to SOC alone.

Part 2

For the analysis of the primary endpoint of Part 2, patients that have not met the endpoint will be censored at Day 28 if they die prior to Day 28. Patients receiving bail-out therapy (as defined in [Section 4.2.2](#)) without having first met the endpoint, will be censored on the day of bail-out. This addresses a hypothetical estimand for the scenario of what would have happened had the bail-out not been administered. Since patients requiring bail-out would be expected to be those already deteriorating, this non-informative censoring could be considered a conservative approach to assessing this estimand. Patients who have not had clinical improvement by Day 28 will be censored on Day 28.

A cox proportional hazards model will be used to estimate the hazard ratio comparing alteplase to SOC alone. From this model, the 95% confidence interval and corresponding Wald p-value for this HR will be produced. In the NIV cohort, adjustment will be made for the number of days under NIV support, baseline D-Dimer level and age. For the IMV cohort, adjustment will be made for the baseline WHO value, baseline D-Dimer level and age.

The Cox proportional hazard model assumptions will be checked.

Kaplan Meier estimates will be presented for this endpoint up to Day 28.

In anticipation of the rare situation where bail-out therapy may be used, as defined in [Section 4.2.2](#), two non-confirmatory supplementary analyses will be conducted, addressing the treatment policy estimand and a composite estimand whereby bail-out represents treatment failure and thereby, by definition, precludes any response after bail-out.

In the first of these supplementary analyses, addressing the treatment policy estimand, there will be no consideration for the intake of bail-out therapy.

In the second of these supplementary analyses, addressing the composite estimand, patients receiving bail-out therapy will be censored at Day 28, rather than on the day of bail-out.

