6.7 BASELINE, TIME WINDOWS AND CALCULATED VISITS

Randomisation is defined as Day 1 and it is planned that the alteplase patients are administered their initial 2h infusion of study medication within 6 hours of randomisation, on Day 1 (Visit 2a). The last planned administration of study medication for the alteplase patients is the long term 12h infusion on Day 5.

Since all patients are on SOC and there is no clear start or stop of SOC, a fixed treatment duration will be used for all patients, for the purposes of the analyses. Therefore, endpoints referred to as ‘on treatment’ will include all relevant events from the relevant start point plus 288 hours (last planned treatment on Day 5 + 7 days of REP = 12 days = 288 hrs).

However, to take account of the fact that some patients may have had treatment interruptions, the residual effect period should be in relation to the last intake of alteplase infusion. [Table 6.7: 1](#) below outlines the time period definitions for counting on treatment safety event.

Table 6.7: 1 Time period for counting on treatment safety events

On treatment	Start point	End date
SOC patients	Randomisation date/time	Start point + 288 hrs
Alteplase patients	First administration of alteplase date/time	Latest of: 
 Start point + 288 hrs Last administration of alteplase date/time + 168 hrs

[Note: 288 hrs represents 12 days, 168 hrs represents 7 days]

According to CTP Version 3 Section 1.2, the residual effect period (REP) is 7 days.

As outlined in CTP Version 3 Section 7.2.1, the term "baseline" refers to the last observed measurement prior to randomisation on Day 1.

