7. PLANNED ANALYSIS

The tables that are created from the statistical analysis will follow the format of the standard within BI [\(8\)](#).

The overall disposition of the patients in the trial will be presented, together with the number of patients discontinuing prior to day 28, and vital status at day 90.

The number of patients participating in the study by country and the number of sites, for each of the patient populations will be summarised.

Demography and baseline characteristics will be presented, as well as the stratification used at the time of the patient randomisation. A summary of the iPDs will be provided.

Where statistical comparisons are indicated, they will be done by comparing alteplase versus SOC.

All descriptive analyses will be performed:

- within the NIV patient cohort as the main cohort
- within the IMV patient cohort as the exploratory cohort
- on the NIV and IMV cohorts pooled – additional select efficacy analyses for primary and secondary efficacy endpoints

For the NIV patient cohort, the default set of covariates for adjustment in analyses are:

- Baseline D-Dimer status (≥ 3 to < 5 , ≥ 5 -fold ULN)
- Age
- Number of days of NIV support
- Baseline value of the $\text{PaO}_2/\text{FiO}_2$ ratio – only for the endpoint $\text{PaO}_2/\text{FiO}_2$ ratio change from baseline to Day 6

For the IMV patient cohort, the default set of covariates for adjustment in analyses are:

- Baseline D-Dimer status (≥ 3 to < 5 , ≥ 5 -fold ULN)
- Age
- Baseline WHO value (7, 8, 9)
- Baseline value of the $\text{PaO}_2/\text{FiO}_2$ ratio – only for the endpoint $\text{PaO}_2/\text{FiO}_2$ ratio change from baseline to Day 6

For efficacy analyses, patients will be analysed according to the patient information given in the CRF, in the case of potentially erroneous data entered into the interactive response technology (IRT). This is related to the baseline information, ventilation support (NIV, IMV) and D-Dimer level (≥ 3 to < 5 , ≥ 5 -fold ULN).

In general, for End-Of-Text tables, the set of summary statistics is: N (number of patients with non-missing values) / Mean / SD / standard error (SE) / Min / Q1 (lower quartile) / Median / Q3 (upper quartile) / Max.

Statistical parameters will be displayed to a defined number of decimal places as specified in the BI guideline "Reporting of Clinical Trials and Project Summaries" [\(9\)](#).

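### Add baseline PaO2/FiO2 to the pooled ANCOVA of PaO2/FiO2 change so that it matches the cohort models; as an optional extra, consider it as a fourth covariate in the confirmatory NIV models

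*Protocol*

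**What the plan says.** **Confirmatory NIV models.** Protocol 7.2.2 states for the primary endpoint: "In the NIV cohort, adjustment will be made for the number of days under NIV support, baseline D-Dimer level and age". Section 7.2.3 repeats the set for treatment failure and mortality, and Section 7.1 ties the endpoints together: "Adjustment will be made for the same set of default covariates as in the primary analysis of the primary endpoint". The synopsis agrees. Part 2 SAP Section 7 lists the same three covariates as the NIV default. It adds baseline PaO2/FiO2 with a restriction, "only for the endpoint" of PaO2/FiO2 change to Day 6.

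**Severity within the cohort.** Protocol Section 7 defines the NIV cohort by a single score: the "patient cohort are those with a baseline WHO value of 6". Inclusion criterion 2 (Section 3.3.2) requires a PaO2/FiO2 ratio, measured or estimated from SpO2, above 100 and at most 300.

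**Baseline.** Protocol 7.2.1 says the term "refers to the last observed measurement prior to randomisation for all patients". Part 2 SAP 6.7 says it "refers to the last observed measurement prior to randomisation on Day 1".

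**PaO2/FiO2 change.** Part 2 SAP 7.5.2 describes two ANCOVAs. The cohort-level text puts the baseline ratio in the model for this endpoint. The later paragraph on the pooled cohorts covers all three continuous endpoints and lists treatment, D-dimer status, age and ventilation status only.

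**The concern.** The WHO score cannot separate patients within the NIV cohort, so the confirmatory models have no direct adjustment for gas exchange at entry, although the value is already collected. In the IMV cohort the baseline WHO covariate carries some of this information, because scores 7 and 8 are split partly at a PaO2/FiO2 of 150 (Protocol Table 5.1.1:1).

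If baseline PaO2/FiO2 is prognostic beyond days under NIV support, D-dimer and age, a little power is left unused. In the pooled analysis of PaO2/FiO2 change, omitting the baseline of the outcome itself can widen the interval, weaken the homogeneity test built on that model, and make the pooled model differ from the two cohort models.

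**Working it through.** **1. The plan's own power (Protocol 7.5).** Inputs: 140 alteplase and 70 SOC patients, two-sided 5%.

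- Primary: 0.30 × 70 + 0.50 × 140 = 91 events. Schoenfeld: √(91 × 2/3 × 1/3) × ln 2.0 − 1.96 = 4.497 × 0.693 − 1.96 = 1.157, so power is 87.6%. With the hazard ratio implied by 30% and 50%, ln 0.5 / ln 0.7 = 1.94, it is 84.8%.
- Treatment failure, 40% vs 20% (28 + 28 = 56 events): null SE 0.0647, alternative SE 0.0676. (0.20 − 1.96 × 0.0647) / 0.0676 = 1.08, so 86.0%.
- Mortality, 25% vs 9% (17.5 + 12.6, about 30 deaths): null SE 0.0513, alternative SE 0.0571. (0.16 − 1.96 × 0.0513) / 0.0571 = 1.04, so 85.1%.

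No covariate enters these figures, and they agree with the stated 85% to 90% and 85%.

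**2. Pooled ANCOVA of change.** Let ρ be the baseline-to-Day-6 correlation and k the Day 6 SD divided by the baseline SD. The residual variance of change, in units of the baseline variance, is k² + 1 − 2ρk without the baseline value and k²(1 − ρ²) with it. The ratio of interval widths is √[(k² + 1 − 2ρk) / (k²(1 − ρ²))]. The documents give neither ρ nor k, so both are assumed.

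| | ρ = 0.3 | ρ = 0.5 | ρ = 0.7 |
|---|---|---|---|
| k = 1 | 1.24 | 1.15 | 1.08 |
| k = 1.5 | 1.07 | 1.02 | 1.00 |

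For example, with k = 1 and ρ = 0.3: √(1.4 / 0.91) = 1.24. The loss is smaller if ventilation status already explains part of the baseline ratio.

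**3. NIV covariate set.** The documents give no prognostic strength, so a hazard or odds ratio of 1.0 to 1.5 per SD is assumed. Simulation: 10,000 runs per scenario at 140/70, calibrated to the event rates of Section 7.5. Both models carry age, D-dimer and days under NIV support; the comparison is with and without PaO2/FiO2. The planned covariates were either non-prognostic and independent, or prognostic at 1.2 each with age and days under NIV support correlated 0.3 with PaO2/FiO2. Change in power, in points:

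| | 1.0 per SD | 1.2 per SD | 1.5 per SD |
|---|---|---|---|
| Primary | −0.2 to +0.1 | +0.5 to +0.6 | +2.8 to +2.9 |
| Treatment failure | −0.1 to 0.0 | +0.1 to +0.4 | +0.8 to +1.1 |
| Mortality | −0.2 to 0.0 | +0.3 | +0.9 to +1.0 |

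- The 95% Monte Carlo error of these differences is at most 0.5 points (primary) and 0.35 (binary). A further Cox simulation gave about +0.2, +1.4 and +2.6.
- If 30% of the covariate's variance is measurement error, the changes at 1.2 and 1.5 are +0.4 and +1.8 (primary), −0.2 and +0.4 (treatment failure), +0.3 and +0.6 (mortality).
- In simpler models with treatment alone or treatment plus PaO2/FiO2, the SE of the log hazard ratio was about 0.252 without the covariate and 0.253 with it. The primary gain therefore comes from a larger conditional log hazard ratio. In the 10,000-run set the average estimated hazard ratio moved from 1.98 to 2.00 at 1.2 per SD and from 1.99 to 2.05 at 1.5.
- For the risk differences the SE does fall. At log odds ratios of 0.3 and 0.5 per SD (odds ratios 1.35 and 1.65), treatment failure goes from 0.0672 to 0.0665 and 0.0654, and mortality from 0.0566 to 0.0562 and 0.0554. That is about 1% to 3%.
- Type I error without vs with the covariate: Cox 5.0% vs 5.3%, treatment failure 5.5% vs 5.6%, mortality 5.7% vs 5.8% (Monte Carlo error about 0.45 points).

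Simulated primary power without the covariate (79% to 83%) is below the Schoenfeld value because events split 21 to 70. That is a separate matter, so only paired differences are used here.

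**The case against.** The confirmatory covariate set is consistent throughout, and the choice looks deliberate. Part 2 SAP Section 7 names baseline PaO2/FiO2 and restricts it to one endpoint. The set was revised after the Part 1 analysis (Protocol 11.2), when the sponsor held PaO2/FiO2 data. A reader might infer that the covariate was overlooked; the documents do not support that. They show no reason for the restriction, but an unstated reason is not a defect.

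The gain rests on assumption. At 1.2 per SD it is close to simulation error, and the eligibility range limits the covariate's spread. The Cox type I difference of 0.3 points, itself within error, would alone add about 0.7 points near 80% power. These points stand, and they are why the NIV change is only an option.

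The value to use is not obvious. The qualifying ratio is the worst in the screening period and the CRF holds the worst of each day (flow chart footnote 9, Protocol 5.1.3), whereas baseline is the last value before randomisation. The Part 1 SAP (6.7) notes that a Day 1 value cannot always be placed before randomisation. This stands, so the fix must name the value.

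The trial is open-label and individual treatment is in the database (SAP 8.1). By-arm tables are withheld until the snapshot (SAP 8.2), so a change can still be pre-specified, but it needs a written record.

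The cohort-level sentence in SAP 7.5.2 could be read as reaching the pooled model. The pooled paragraph gives its own list without the baseline value, so a clarifying line is still needed.

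SAP Section 6.4 is not visible. An exploratory PaO2/FiO2-adjusted run may exist under SAP 7.4.2, but it would not alter the confirmatory model.

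**Conclusion.** Optional improvement, not an error. A reader might infer that omitting the covariate makes the confirmatory tests invalid or the trial underpowered. It does neither: the randomised comparison is valid without it, and the stated powers reproduce with no covariate. A reader might also expect a tighter hazard ratio; the standard error does not fall.

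The firm part is the mismatch in SAP 7.5.2. Leaving the baseline value out of the pooled model costs 8% to 24% in interval width with equal SDs, or 0% to 7% if the Day 6 SD is 1.5 times the baseline SD. The analysis is exploratory, and ρ and k are assumed.

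The NIV covariate is a cheap option worth about 0 to 3 points of power on the primary test and about 0 to 1 point on the key secondary endpoints, with slightly tighter risk-difference intervals, at an assumed 1.0 to 1.5 per SD. Larger gains need stronger prognostic effects, which the documents do not support. If the covariate is not prognostic, almost nothing is lost.

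**What to change.** **Firm.** In the pooled paragraph of Part 2 SAP 7.5.2, add baseline PaO2/FiO2 to the model for PaO2/FiO2 change. Cost: one line.

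**Optional, before the Day 28 snapshot is unblinded.**

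- Add continuous baseline PaO2/FiO2 to the NIV covariate set for the primary and both key secondary endpoints, since Protocol 7.1 requires a common set.
- State that it is the last value recorded before randomisation, that the screening value is used when the timing of a Day 1 value is uncertain, and that SpO2-inferred values are used as recorded.
- Keep the three-covariate model as a sensitivity analysis.
- Record that no by-arm outcome data informed the change.

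Cost: text edits in the synopsis, Protocol 7.1 to 7.2.3 and SAP Section 7, and no new data. The Part 2 SAP was written to protocol Version 3 and still carries the 3-fold lower D-dimer bound, so it needs revision anyway. The oxygen-free-days and hospital-stay ANCOVAs use the same default set and would follow.

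Downsides: one more parameter with only about 30 expected deaths; some SpO2-inferred values, with saturations of 97% to 100% flagged as unreliable in Appendix 10.2; and a hazard ratio that conditions on one more covariate. If the sponsor keeps the restriction on purpose, a sentence giving the reason would settle the optional part.

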A sensitivity analysis of the primary endpoint (main estimand) will be carried out on the PPS, in line with the primary analysis.

Following the amendment to the inclusion criteria (CTP Version 4.0), whereby the original D-Dimer level changed from ≥ 3 -ULN to \geq ULN, some additional analyses will be performed. Firstly, a sensitivity analysis will be added, similar to the primary analysis, just replacing the baseline D-Dimer status on the two levels with that on the three levels (\geq ULN to < 3 , ≥ 3 to < 5 , ≥ 5 -ULN). Secondly, a supplementary analysis will be added, similar to the primary analysis, but removing all patients with baseline D-dimer status \geq ULN to < 3 -ULN, which is according to the expanded inclusion criteria.

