Rationale for change	Use of mixture of remote and on-site visits to increase quality of data collection.
Section to be changed	Appendix 10.4
Description of change 61	
Dosing regimen A (lower dose) dosing table (only applicable in Part 1 of the trial)
 
Dosing regimen B (higher dose) dosing table (applicable in both Parts of the trial)

Rationale for change	Reflecting decision on the trial – dosing regimen B for Part 2
Section to be changed	Appendix 10.5
Description of change 62	A list of guideline-recommended therapies for COVID-19 specifically, and for critically ill patients in general was added
Rationale for change	Standardization of SOC therapy across participating study sites by providing guideline recommended treatment recommendations

11.3 GLOBAL AMENDMENT 3

Date of amendment	17 Feb 2022
EudraCT number	2020-002913-16
EU number	
BI Trial number	0135-0347
BI Investigational Product(s)	Alteplase (recombinant tissue-type plasminogen activator, rt-PA)
Title of protocol	
The TRISTRADS trial - ThRombolysis Therapy for ARDS
 
A Phase IIb/III operationally seamless, open-label, randomised, sequential, parallel-group adaptive study to evaluate the efficacy and safety of daily intravenous alteplase treatment given up to 5 days on top of standard of care (SOC) compared with SOC alone, in patients with acute respiratory distress syndrome (ARDS) triggered by COVID-19.

Global Amendment due to urgent safety reasons	
Global Amendment	X
Section to be changed	Protocol synopsis
Description of change	D-Dimer levels (\geq 3-fold to <5-fold ULN, versus \geq 5-fold ULN) updated to Randomisation will be stratified by D-Dimer levels (\geq ULN to <5-fold ULN, versus \geq 5-fold ULN) updated from
Rationale for change	Stratification factor adapted based on the changed inclusion criterion of D-Dimer level \geq ULN.
Section to be changed	Protocol synopsis
Description of change	Inclusion criteria #4 updated: Fibrinogen level \geq lower limit of normal
Rationale for change	Alteplase results in a modest decrease of the circulating plasma fibrinogen levels. Fibrinogen levels \geq ULN were previously required as an inclusion criterion to ensure that fibrinogen levels are high enough and are less likely to decrease to a critical level below 150 mg/dL which have been

Clinical Trial Protocol

Page 136 of 140

Proprietary confidential information © 2022 Boehringer Ingelheim International GmbH or one or more of its affiliated companies

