Description of change	Added : Following the amendment to the inclusion criteria (CTP Version 4.0), whereby the original D-Dimer level changed from \geq 3-ULN to \geq ULN, some additional analyses will be performed. Firstly, a sensitivity analysis will be added, similar to the primary analysis, just replacing the baseline D-Dimer status on the two levels with that on the three levels (\geq ULN to <3 , \geq 3 to <5 , \geq 5-ULN). Secondly, a supplementary analysis will be added, similar to the primary analysis, but removing all patients with baseline D-dimer status \geq ULN to <3 -ULN, which is according to the expanded inclusion criteria.
Rationale for change	Consistent with section 3.1, 4.1.3 and 7 The sensitivity and supplementary analyses have been added, to account for the change to the study population, and to adjust for or assess the impact of the changes.
Section to be changed	Section 7.4 Randomization
Description of change	Updated wording reflecting D-dimers update: Randomisation in Part 2 will be to alteplase and to standard of care, with an allocation ratio of 2:1, with stratification by the following factors: 
• Type of ventilation (non-invasive or invasive mechanical)• D-Dimer levels (\geqULN to <5-fold ULN, versus \geq5-fold ULN)

Clinical Trial Protocol

Page 140 of 140

Proprietary confidential information © 2022 Boehringer Ingelheim International GmbH or one or more of its affiliated companies

Rationale for change	Reflecting update for D-dimer level requirements
Section to be changed	Section 8.3.2
Description of change	Updated: During the conduct of the study, it may not be possible for the investigator / institution to allow site trial-related monitoring, audits, IRB/EC review or regular inspections due to COVID-19 restrictions.
Rationale for change	Typo for IRB and added restrictions for COVID-19 for clarity
Section to be changed	Appendix 10.1
Description of change	Glasgow coma scale added
Rationale for change	Mistakenly removed in previous version
Section to be changed	Appendix 10.3
Description of change	Added Appendix: FiO ₂ ranges for common oxygen delivery devices
Rationale for change	Additional instructions provided, consistency with Section 5.1.3
Section to be changed	Table10.6:1 Treatment Recommendations for COVID-19 ARDS (with a focus on NIV Patients)

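### The supplementary analysis added after Amendment 3 screens out newly eligible D-dimer patients but not newly eligible fibrinogen patients, and the visible plan does not break major bleeding down by baseline fibrinogen

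*Protocol*

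**What the plan says.** Protocol 7.2.2 describes the amended inclusion criteria by the D-dimer change alone and adds two analyses of the primary endpoint. The first is a sensitivity analysis with D-dimer at three levels instead of two. The second reads: "Secondly, a supplementary analysis will be added, similar to the primary analysis, but removing all patients with baseline D-dimer status" from ULN to below 3-fold ULN.

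The rationale in Protocol 11.3 for this addition is "to account for the change to the study population, and to adjust for or assess the impact of the changes".

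The same amendment changed inclusion criterion 4. According to Protocol 11.3, fibrinogen levels at or above "ULN were previously required as an inclusion criterion to ensure that fibrinogen levels are high enough", so that a fall below 150 mg/dL, a level associated with bleeding, would be less likely. The current criterion in Protocol 3.3.2 asks only for a level at or above the local LLN. The amendment supports the change by daily fibrinogen monitoring and an interruption rule. It names no analysis.

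On bleeding, Protocol 7.2.3 and Part 2 SAP 7.5.2 compare major bleeding to Day 6 between arms by an exact method without covariates. Part 2 SAP section 4 limits the subgroup analyses to the primary endpoint and one secondary endpoint, which 7.5.2 identifies as PaO2/FiO2.

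**The concern.** Two laboratory thresholds moved together and the restricted analysis reverses one of them. Its result may be taken as the effect in patients who would have entered under the earlier laboratory rules, yet the cut cannot ensure that. The comparison matters because the Part 2 dose choice and the sample size assumptions lean on Part 1 (Protocol 1.1 and 7.5), Protocol 3.1 says that both parts include the same population, and pooled summaries of the two parts are planned (Protocol 7.2.1, Part 2 SAP section 3).

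Fibrinogen also has a safety side. The earlier threshold was explained as protection against a bleeding-associated fall. When such a threshold is relaxed, the natural descriptive question is how major bleeding looks in the patients whom the change let in. The visible plan does not ask it.

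**Working it through.** The finding is textual. The amendment log is used here only as evidence of what changed, not as text that conflicts with the current protocol.

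**1. Who is kept.** Cross the two thresholds, using baseline values:

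| | Fibrinogen LLN to <ULN | Fibrinogen >=ULN |
|---|---|---|
| D-dimer ULN to <3-fold | newly eligible on both; removed by 7.2.2 | newly eligible on D-dimer; removed by 7.2.2 |
| D-dimer >=3-fold | newly eligible on fibrinogen; **kept by 7.2.2** | met both earlier thresholds; kept |

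The lower left cell is the gap. The three-level D-dimer covariate does not separate it either.

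**2. Effect on the estimate.** The size of that cell is not given, so any figure is an assumption. If a share s of the events in the restricted set comes from it with hazard ratio h, and the rest have the planned 2.0, then roughly

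pooled HR = exp[(1 - s) ln 2.0 + s ln h].

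- s = 0.1, h = 1.5: 1.94
- s = 0.2, h = 1.0: 1.74
- s = 0.3, h = 1.0: 1.62

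If s = 0 there is no effect, and h could also exceed 2.0. The documents fix neither.

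**3. Cost of a joint cut in precision.** First the plan's own figure (Protocol 7.5: 70 SOC and 140 alteplase, event rates 30% and 50%, HR 2.0, two-sided 5%, power 85% to 90%).

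- Events: 70 x 0.30 + 140 x 0.50 = 21 + 70 = 91.
- Schoenfeld: power = Phi{sqrt[91 x (1/3) x (2/3)] x ln 2.0 - 1.96} = Phi(4.497 x 0.693 - 1.96) = Phi(1.157) = 0.876, inside the stated range.

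With a share f of the 210 NIV patients retained, unchanged event rates and 91f events:

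| f | n | Events | Power at HR 2.0 |
|---|---|---|---|
| 0.9 | 189 | 81.9 | 0.841 |
| 0.8 | 168 | 72.8 | 0.796 |
| 0.7 | 147 | 63.7 | 0.741 |
| 0.6 | 126 | 54.6 | 0.675 |
| 0.5 | 105 | 45.5 | 0.596 |

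The restricted analysis is not confirmatory, so power here only shows how information shrinks. The D-dimer-only cut loses some of it already.

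**4. Would a bleeding table hold anything?** Part 1 had 4 (Protocol 1.1) or 3 (Protocol 1.4.2) patients with major bleeding to Day 6 at the dose taken forward. The denominator is 20, since 12 patients are given as 60.0% and 12/0.60 = 20. That is 15% to 20%. Applied to 140 NIV alteplase patients it gives 140 x 0.15 = 21 to 140 x 0.20 = 28 events. If, by assumption, 20% of the arm (28 patients) had fibrinogen from LLN to below ULN, about 4 to 6 events would fall there. The exact 95% intervals are 4.0% to 32.7% for 4/28 and 8.3% to 41.0% for 6/28. The table would not be empty, but it would be descriptive only. That Part 1 used the ULN fibrinogen threshold is inferred: Amendments 1 and 2 list no change to it.

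**The case against.** Several points on the other side stand.

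- **Purpose.** A reader might infer that the analysis was meant to undo the whole amendment. Protocol 7.2.2 does not say that; it frames both analyses around D-dimer and does what it states. The wider purpose appears only in the rationale in 11.3, which also refers to consistency with sections whose changes were to the D-dimer stratum. There is a design reason to single out D-dimer: it is a stratification factor and a model covariate, and fibrinogen is neither. Even so, the rationale speaks of the study population, and fibrinogen entry changed as well.
- **Contents of the set.** A reader might infer that the restricted set does hold newly eligible patients. The documents show only that it can.
- **Bleeding.** A reader might infer that bleeding after the change goes unexamined, or that no analysis could show harm. That is not supported. Newly eligible treated patients are in the Treated Set, so excess bleeding among them enters the arm comparison. The DMC reviews unblinded safety data and may recommend changes to entry criteria (Protocol 3.2). Fibrinogen is monitored daily. Only the breakdown is missing.
- **Unseen text.** The Part 2 SAP is dated 26 October 2021 and follows CTP Version 3. The amendment is dated 17 February 2022, so that SAP could not respond to it. No SAP for Version 4.0 was supplied, and SAP 5.3 and 6.4 are not visible.
- **The remedy is partial.** Two laboratory thresholds do not restore the earlier population. Amendment 3 also changed exclusion 1 on pulmonary embolism and the D-dimer sampling window, and Amendment 2 added or altered other exclusions.

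**Conclusion.** The point holds as a gap in coverage. Two laboratory thresholds were lowered, the supplementary analysis handles one, and patients newly eligible only through fibrinogen stay in the restricted set. Measured against the aim in Protocol 11.3, the analysis is incomplete. In the visible text no planned output relates major bleeding to baseline fibrinogen, although the earlier threshold had a stated bleeding rationale.

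The size is unknown, because it depends on how many patients have D-dimer at or above 3-fold ULN and fibrinogen from LLN to below ULN. The hazard ratios and bleeding counts in the working are illustrations under stated assumptions. The statement about bleeding is limited to the text supplied. The primary test, alpha, sample size and testing hierarchy are untouched, so this is a low-cost improvement and not a flaw in the confirmatory analysis.

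**What to change.** In Protocol 7.2.2 and the SAP update for Version 4.0:

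1. Define the supplementary set as patients who meet both earlier laboratory thresholds: baseline D-dimer at or above 3-fold ULN and baseline fibrinogen at or above ULN, each against the local range. Keep the D-dimer-only cut as a second version, labelled as such.
2. Describe the result as restricted to the earlier laboratory thresholds, not as the full earlier population.
3. Add one descriptive table of major bleeding to Day 6 by arm and baseline fibrinogen (LLN to <ULN versus >=ULN).

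Fibrinogen is already measured at screening (Flow Chart), and local reference ranges are held (Protocol 5.2.3). The cost is wording, two extra non-confirmatory outputs, and a smaller and less precise supplementary set. No entry criterion or clinical rule changes.
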